#### 8.1.2 Primary and secondary analyses

##### Statistical methods:

Study data will be analysed descriptively. No formal hypothesis testing is planned.

All parameters will be analysed for the per protocol population using descriptive statistics including confidence intervals whenever appropriate. Details will be defined in a statistical analysis plan (SAP), which will be signed prior to unblinding of the samples.

Descriptive statistical methods will be used to summarise the results of the study. The following descriptive statistics will be calculated for continuously distributed data and for ordered categorical data (ordinal data) if applicable:

- N (number of non-missing measurements)
- Arithmetic mean
- Standard deviation
- Coefficient of variation (CV),
- Geometric mean

- Geometric standard deviation (re-transformed standard deviation of the logarithms)
- Corresponding CV
- Minimum
- Median
- Maximum

For ordered categorical data and nominal data, absolute and relative frequencies (in %) will be calculated.

Group or stratification variables due to the study design are:

- GdCA test group or control
- Renal function category (moderate impairment, severe impairment or stable normal renal function eGFR > 60 ml/min/1.73 m^2, Figure 3)
- Single (one injection of standard dose) or multiple (more than one injection or one injection with higher than standard) doses of GdCA administered

The elapsed time from dosing of GdCA until surgery will be classified and will also be used for stratification.

Statistical tables will compare all GdCA groups pooled as well as each GdCA group separately versus the control group. They will be further stratified according to renal function category (3 groups), single / multiple doses of all patients (2 groups), and the combination of “renal function with “single / multiple doses”.

The primary analysis encompasses the evaluation of Gd concentration in trabecular and cortical bone. The secondary analysis deals with Gd concentration in skin as well as the parameters specified below.

Descriptive analyses include

- Gd concentration in bone (trabecular and cortical) and skin will be expressed as nmol Gd / g bone or skin.
- Gd concentration in bone (trabecular and cortical) and skin as a function of time elapsed between GdCA injection and surgery. Additional stratification classifications of time after dosing of Gd will be specified in the SAP.

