8.3 Analysis Set

Analysis Set	Definition
Screening population	All subjects who entered the study
Safety analysis set (SAF)	All subjects who have undergone the planned orthopedic surgical procedure
Full analysis set (FAS)	All subjects in the SAF for whom Gd measurements from the bone are available
Per protocol set (PPS)	
All subjects in the FAS who meet the defined requirements of GBCA treatment history, all inclusion and exclusion criteria, and whose tissue samples yield data for Gd in bone (trabecular as well as cortical) and skin.
 
The evaliability of subjects /samples shall be assessed by a blinded data review prior to final unblinding and analysis.

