8.7 Interim Analysis

At the request of the EMA, an interim analysis was to be carried out on all subjects enrolled in the single dose subgroups for Gadobutrol, Gadoteric acid, Gadodiamide, and Gadopentetic acid once at least three subjects had been recruited to the single-dose subgroups for the 4 agents as well as on all subjects of the control group (naïve subjects).

A total of 55 subjects were eligible for the IA. Due to the fact, that the laboratory data for these subjects had to be unblinded, these subjects have already been classified before IA evaluation with regard to PDs. Since one subject had no concentration data available, only 54 subjects were included in the SAF.

To determine the Gd concentration in bone (trabecular and cortical) and skin (expressed as $\mu\text{g Gd / g}$) the IA based on the SAF and Gd concentrations was descriptively evaluated by:

- Renal function status: stable normal renal function ($\text{eGFR} > 60 \text{ ml/min/1.73 m}^2$),
 at least moderate impaired renal function ($\leq 60 \text{ ml/min/1.73 m}^2$)
- GBCA: Each of the 4 GBCAs (Gadobutrol, Gadoteric acid, Gadodiamide, and Gadopentetic acid) and control

No statistical tests have been calculated.

All data used in the interim analysis have been listed. All listings including subject identifier, GBCA type, renal function, and have been sorted by GBCA type, renal function, and subject identifier. Study investigational sites and analytical laboratories have been blinded to the IA results.

Details on the IA evaluation have been described in the interim SAP and the Abbreviated Interim Analysis Report, Version Final 1.0, dated 20181108.

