9.6.2 Secondary Analysis

The secondary evaluation parameter Gd concentration in skin (expressed as µg Gd /g) will be analyzed for the FAS analogously to the primary parameter.

For the following secondary parameter number and percentages or arithmetic summery statistics will be presented for the FAS where applicable.

- Time elapsed between most recent administration of GBCA and surgery in month
- Time of cumulative GBCA doses [month]
- Potential co-factors for NSF and susceptibility factors, based on the following data and in the limit of their availability in medical history of the subjects:
 - eGFR
 - cumulative dose of GBCA
 - co-existing vascular, thrombotic and/or pro-inflammatory events
 - serum concentrations of calcium, phosphorus, sodium, iron, potassium and zinc

Sponsor Name: Navitas Life
 Sciences GmbH
 Statistical Analysis Plan (SAP)
 Version No.: Final 1

Short Title of Study: Long-Term Retention of
 Gadolinium in Bone
 Sponsor Study No.: ALS-Gd64/001
 Date: 31JUL2019
 NLS Study No.: 665

- any event which may have led to iron mobilization, including concomitant iron drug
- cumulative dose of erythropoietin
- T4 and TSH.
- Concomitant drug treatments with potential impact on bone metabolism: biphosphonates, estrogens, calcitonin, calcitriol, fluoride salts, vitamin D, corticosteroids.
- Concentration of Ca, P, Na, Zn, K and Fe in skin and in tissue of both trabecular and cortical bone determined by ICP-MS.

No statistical tests will be calculated.

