14 LIST OF REPORTED TABLES

Tables will be numbered within their section in ascending order. In this SAP the numbering of all TLFs is done according to the ICH guidelines.

Note that TLFs in this SAP may differ slightly from the layout of the IA SAP tables. That is due to the fact that the IA SAP was created according to the old ECRON ACUNOVA standard and the current SAP is written according to the Navitas Life Science standard.

No.	Title	Analysis Set	Corresponding Table in the IA
14.1	Subject Disposition	All Subjects	
14.1.1	Subject Disposition	Applicable	A 1
14.2	Demographic Data and Baseline Characteristics	SAF, FAS, PPS	
14.2.1	Demographic Characteristics	Applicable	A 2.1 – A 2.5
14.2.2	Baseline Characteristics - Diagnosis of Qualifying Study Indication	Applicable	Not Applicable
14.3	Medical History and Concomitant Diseases	SAF	
14.3.1	Relevant Medical History	Applicable	Not Applicable
14.3.2	Concomitant Diseases	Applicable	Not Applicable
14.4	Previous and Concomitant Medications	SAF	
14.4.1	Prior Medication and Therapies	Applicable	Not Applicable
14.4.2	Concomitant Medication and Therapies	Applicable	Not Applicable
14.5	Orthopedic surgery	SAF	

Sponsor Name: Navitas Life
Sciences GmbH

Statistical Analysis Plan (SAP)

Version No.: Final 1

Date: 31JUL2019

Short Title of Study: Long-Term Retention of
Gadolinium in Bone

Sponsor Study No.: ALS-Gd64/001

NLS Study No.: 665

No.	Title	Analysis Set	Corresponding Table in the IA
14.5.1	Bone and Tissue Sampling	Applicable	Not Applicable
14.6	Analysis	FAS, PPS	
14.6.1	Primary Analysis	Applicable	
14.6.1.1	Gadolinium Concentration in Trabecular Bone by Renal Function Status	Applicable	A 3.1.1 – A 3.1.5
14.6.1.2	Gadolinium concentration in Cortical Bone by Renal Function Status	Applicable	A 3.1.7 – A 3.1.11
14.6.2	Secondary Analysis	PPS	
14.6.2.1	Gadolinium concentration in Skin by Renal Function Status	Applicable	A 3.2.1 – A3.2.5
14.6.2.2	Time between last Administration of GBCA and the Date of Tissue Sample Collection	Applicable	Not Applicable
14.6.2.4	Individual eGFR values	Applicable	Not Applicable
14.6.2.5	Potential Co-Factors for NSF and Susceptibility Factors	Applicable	Not Applicable
14.6.2.6	Concomitant Drug Treatments with Potential Impact on Bone Metabolism	Applicable	Not Applicable
14.6.2.7	Concentration of Ca, P, Na, Zn, K and Fe in skin and in tissue of both trabecular and cortical bone determined by ICP-MS	Applicable	Not Applicable

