14.6.2.8	Histopathological evaluation of skin samples (taken at time of surgery / surgeries) with regard to the possibility of findings associated with NSF	Applicable	Not Applicable
14.7	Adverse Events	SAF, FAS, PPS	
14.7.1	Summary of Adverse Events	Applicable	Not Applicable
14.7.2	Adverse Events by System Organ Class and Preferred Term (MedDRA Version x.x)	Applicable	Not Applicable
14.7.3	GBCA Related Adverse Event by System Organ Class and Preferred Term (MedDRA Version x.x)	Applicable	Not Applicable
14.7.4	Serious Adverse Events by System Organ Class and Preferred Term (MedDRA Version x.x)	Applicable	Not Applicable

Sponsor Name: Navitas Life
 Sciences GmbH
 Statistical Analysis Plan (SAP)
 Version No.: Final 1

Date: 31JUL2019

Short Title of Study: Long-Term Retention of
 Gadolinium in BoneSponsor Study No.: ALS-Gd64/001
 NLS Study No.: 665

No.	Title	Analysis Set	Corresponding Table in the IA
14.7.5	GBCA Related Serious Adverse Events by System Organ Class and Preferred Term (MedDRA Version x.x)	Applicable	Not Applicable
14.7.6	Serious Adverse Events and Death by Subject (MedDRA Version x.x)	Applicable	Not Applicable

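### The SAP's only summary table for the NSF skin-histology objective is tied to Gd assay results and full eligibility, so an evaluable biopsy can go uncounted there, though not unreported

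*SAP*

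**What the plan says.** SAP 8.3 defines three nested sets of operated patients:

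- The SAF is "All subjects who have undergone the planned orthopedic surgical procedure". It carries no assay condition.
- The FAS is "All subjects in the SAF for whom Gd measurements from the bone are available". The text does not say whether one bone compartment is enough.
- The PPS is the part of the FAS that meets the treatment-history requirements and every entry criterion, and "whose tissue samples yield data for Gd in bone (trabecular as well as cortical) and skin".

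Skin Gd, according to SAP 9.6.2, "will be analyzed for the FAS analogously to the primary parameter". The same section puts its other listed secondary parameters on the FAS. Histology is not in that list, although SAP 7.3.1 names it as a secondary parameter and SAP 6.2 makes NSF-type skin change a secondary objective.

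In the table list (SAP section 14), 14.6 is marked FAS and PPS, and the line below it for 14.6.2 reads "Secondary Analysis PPS". That block runs from 14.6.2.1 (skin Gd) to 14.6.2.8, "Histopathological evaluation of skin samples (taken at time of surgery / surgeries) with regard to the possibility of findings associated with NSF". The table list is therefore the only place where the SAP gives histology an analysis set. Protocol 8.1.2 points the same way: "All parameters will be analysed for the per protocol population using descriptive statistics".

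**The concern.** The NSF skin objective asks what the biopsies show. It sets no condition on bone Gd. Protocol 5.1.3 describes the skin biopsy as the only procedure done to patients for the study's own purposes, so each readable biopsy should count towards that objective.

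Under the planned sets, a patient with readable histology is left out of table 14.6.2.8 if any one of three Gd results is missing (PPS) or if bone Gd is missing (FAS). Under the PPS, an eligibility deviation also removes the patient. One such deviation is related to the outcome itself: exclusion criterion 6 (protocol 4.2) covers diagnosed or suspected NSF at enrolment. A patient enrolled despite it would fail the PPS, and that is a patient whose biopsy is more likely than most to show NSF-type change.

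At stake is whether the summary table gives the correct numerator and denominator for a finding that is likely to be rare.

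**Working it through.** This is mainly a matter of tracing definitions.

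**1. Does histology depend on a Gd assay?** Protocol 5.1.3 takes two 5 mm lengths of the skin strip for histology and divides the remainder for bioanalysis. The histology pieces are fixed in formaldehyde and go to the dermatopathology laboratory (protocol 6.1.4.1 and 6.1.4.2). Bone and skin for Gd are frozen and go to the bioanalytical laboratory (protocol 6.1.3.1). Aliquot, preservation and laboratory all differ, so histology can be valid when a Gd result is missing, and the reverse.

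**2. Which results reach which skin table?**

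| Patient has surgery and… | FAS | PPS | In 14.6.2.8 (histology) | In 14.6.2.1 (skin Gd) |
|---|---|---|---|---|
| all three Gd results, eligible | yes | yes | yes | yes |
| histology and skin Gd, no bone Gd | no | no | no | no |
| histology and bone Gd, no skin Gd | yes | no | only if run on FAS | no result to show |
| all three Gd results, eligibility deviation | yes | no | only if run on FAS | only if run on FAS |

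The second row is excluded on every reading. The last two depend on whether FAS or PPS governs, which 9.6.2 and section 14 answer differently. SAP section 10 lets the SAP override the protocol, but that rule cannot settle a conflict inside the SAP. A value below the LLOQ is replaced by half the LLOQ (SAP 8.5), so it is most naturally read as an available result that excludes nobody; the SAP does not say so.

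**3. How many patients?** SAP 8.7 reports 55 subjects eligible for the interim analysis and says "Since one subject had no concentration data available, only 54 subjects were included in the SAF". The subtraction agrees: 55 − 1 = 54, and 1/55 = 1.8%. This shows that missing concentration data occurred. It does not give a rate of readable biopsies excluded, because the histology status of that subject is not stated.

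**4. Weight of one biopsy.** The test-group minimum reproduces as 2 × (5 + 3 + 5 + 3) + 4 × (5 + 0 + 5 + 3) = 32 + 52 = 84, and 84 + 15 controls = 99. Most agent-by-renal-function-by-dose cells therefore hold 3 to 5 patients. One biopsy left out of such a cell is 1/5 = 20% to 1/3 = 33% of it. If the targets count only evaluable patients and the omitted patient is additional to them, it is 1/6 = 17% to 1/4 = 25%.

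**5. Overall precision.** The exact two-sided 95% upper limit for zero events is 1 − 0.025^(1/n). For n = 99 it is 3.7%; for n = 97, chosen only as an illustration, it is also 3.7%. The issue is completeness of the count, not precision.

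**The case against.** The strongest reply is that nothing disappears from the report. SAP section 16 says listings should cover all subjects with data, and a histopathology listing is planned. Protocol 6.1.4.3 sends histology results to the centres so that possible adverse events can be assessed. NSF-like events are serious (SAP 7.3.2), and SAP 9.7 analyses adverse events on the SAF. SAP 9.5 also tabulates, on the SAF, whether a skin sample for histopathology was taken.

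All of this stands. A reader might infer that an NSF-type finding could go from found to not found. The documents do not support that for the report as a whole; it can be true only of table 14.6.2.8.

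These routes do not replace the table, however. A listing gives no count by group. A tally of samples taken is not a tally of samples read. The adverse event route depends on the investigator judging the result to be an event. Recording normally ends at visit 4, about 10 to 14 days after surgery (visit 8 after a second procedure), and no histology turnaround time is stated. A change not judged an event would appear only in the listing.

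A second reply is that protocol 1.1 and 3.1 want skin findings related to bone Gd, for which a common set is natural. That is fair, and for skin Gd it makes the point a matter of preference. But 14.6.2.8 is a histology table, and no correlation table is listed.

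**Conclusion.** The point holds for the summary tables. Table 14.6.2.8 is restricted by conditions unrelated to whether a biopsy can be read, and 9.6.2 omits histology. The same restriction on skin Gd in 14.6.2.1 is a lesser matter. The FAS/PPS conflict between 9.6.2 and section 14 needs resolving in any case.

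The number of patients affected cannot be derived, since the documents give no missing-sample counts by tissue. A reader might multiply 1/55 by 99 and expect about two lost biopsies. The documents do not support that. The interim subject may have had no biopsy: SAP 8.7 leaves that subject out of the SAF, which 8.3 defines by surgery. In addition, the 99 is stated as a number of evaluable patients, so non-evaluable patients may be additional to it.

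The primary bone analysis is unaffected. This is an inexpensive improvement to a stated secondary objective. It rests on at least one patient having readable histology without meeting the FAS or PPS conditions, which is plausible but not documented.

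**What to change.** In SAP 9.6.2 and section 14:

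- Tabulate 14.6.2.8 for all SAF subjects with an evaluable histology sample, showing that N.
- Tabulate 14.6.2.1 for all SAF subjects with a skin Gd result, with its own N.
- Keep the PPS version of each as the restricted repeat.
- Add histology, with its analysis set, to 9.6.2.
- Make 9.6.2 and the 14.6.2 heading agree on the set for the other secondary tables.
- Record the change from the protocol's per-protocol rule in SAP section 10.
- Confirm that the final SAF follows the surgery-based definition in 8.3 and does not drop subjects for lack of concentration data, as 8.7 describes for the interim.

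The cost is SAP wording and one extra run of two tables. The downside is that the N in the skin tables will differ slightly from the N in the bone tables; a footnote can explain this.

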8.4 Protocol Deviation

The relevant protocol deviations (PD) have to be defined by a systematic data review prior to database closure. For this purpose, PDs that occurred during the study such as deviations of inclusion/exclusion criteria or forbidden concomitant medications will be assessed as ‘major’ or ‘minor’ depending on their potential to interfere with the objectives of the study. Listings will be prepared to show the eligibility of all subjects. Comprehensive justification for the classification of a PD as “major” will be given in the integrated clinical study report.

Major protocol deviations and the assessment of analysis sets will be defined during last data review before data base closure. All definitions given in the Minutes of the Final Data Review will be considered in the analysis.

Due to the fact, that the laboratory data for all subjects included in the IA had to be unblinded, these subjects have already been classified before the IA evaluation with regard to PDs.

The list of protocol deviations will be reviewed by the sponsor and finalized before locking the database. The sponsor will identify major protocol violations which will lead to exclusion of subjects from the PPS. Major protocol violations excluded from PPS will be flagged in the protocol violation listing.

8.5 Data Handling

There will be no imputation of missing data. All data will be analyzed as they appear in the data base.

Since the geometric mean (the retransformed mean of the logarithmized values) and CV% cannot be calculated in the presence of zero values, the values BLQ were implemented in the IA analysis by half the LLOQ (i.e. 0.025) instead of zero for the calculation of the descriptive statistics. This approach will also be

Sponsor Name: Navitas Life
 Sciences GmbH
 Statistical Analysis Plan (SAP)
 Version No.: Final 1

Short Title of Study: Long-Term Retention of
 Gadolinium in Bone
 Sponsor Study No.: ALS-Gd64/001
 Date: 31JUL2019
 NLS Study No.: 665

used for the final analysis. Therefore, values below the limit of quantification (LLOQ) will be replaced by half of the LLOQ (i.e 0.025) instead of zero for the calculation of the descriptive statistics. For adverse events the following rules will be applied:

- AEs with unknown onset date/time will be counted as treatment emergent AEs.
- AEs with unknown end date/time will be counted as an ongoing AE.
- AEs with unknown relationship to GBCA will be counted as related in AE summary tables.
- If for the calculation of a time period the full date format ddmmmyyyy is needed, missing entries will be imputed as follows:
 - Missing day in start date of a time period is imputed by the first day of the month;
 - Missing day in stop date of a time period is imputed by the last day of the month;
 - Missing month in start date of a time period is imputed by January of the year;
 - Missing month in stop date of a time period is imputed by December of the year;
 - Missing year is not imputed.

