#### **GdCA naïve patients (control group)**

10. Patient has never received GdCA before the scheduled orthopaedic surgical procedure.

11. Patient belongs to one of the following renal function categories:

- e) patient (total to enrol = 5) has stable severe renal impairment (eGFR  $<$  30 ml/min/1.73 m $^2$ );
- f) patient (total to enrol = 5) has stable moderate renal impairment (eGFR within the range 30 to 60 ml/min/1.73 m $^2$ );
- g) patient (total to enrol = 5) has stable normal renal function (eGFR  $>$  60 ml/min/1.73 m $^2$ ).

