#### 6.2.4.2 Assessment of adverse events

Each AE will be assessed by the investigator regarding potential causal relationship with one or more of the following categories:

- (1) related to the orthopaedic surgery (bone resection included).
- (2) related to the skin biopsy.
- (3) related to GdCA exposure in the past (e.g. NSF signs after enrolment).
- (4) related to other health conditions of the patient.

The investigator must assess each AE as either **unrelated** or causally **related** to any of the categories (1) – (4). Related means possibly, probably or certainly related.

Each AE will be characterised by the investigator according to intensity of the event and whether any of the seriousness criteria apply. The definitions are given below:

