8.9 Definitions and Derived Variables

Variable / Term	Definition / Way of calculation
Test group	Refers to subjects with GBCA exposure
Control	Includes GBCA naïve subjects
Stable normal renal function	Stable normal renal function (eGFR > 60 ml/min/1.73 m ²),
Impaired renal function	Impaired renal function (eGFR <=60 ml/min/1.73 m ²) The groups of sever and moderate impaired renal function are combined as explained in the section 10.
Single dose	Only one application of GBCA (0.1 mmol per kg body weight for Gadobutrol, Gadoteric acid, Gadodiamide, and Gadopentetic acid; 0.025 mmol per kg body weight for Gadoxetic acid)
Multiple dose	More than one application of GBCA or one injection with higher than approved standard dose (0.1 mmol per kg body weight for Gadobutrol, Gadoteric acid, Gadodiamide, and Gadopentetic acid; 0.025 mmol per kg body weight for Gadoxetic acid))
Time between most recent administration of GBCA [month] and surgery	= (Date of surgery – date of most recent GBCA administration +1 day) / 30.25
Time of cumulative GBCA doses [month]	= (Date of surgery – date of first GBCA administration +1 day) / 30.25
Cumulative dose of GBCA (mmol)	= Sum of all administrated GBCA doses
Cumulative dose of erythropoietin [IU/L]	= Sum of all administrated erythropoietin doses

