17 MOCKUPS OF TABLES AND SUBJECT DATA LISTINGS

Please note: Yellow resp. cursive texts are working advices.

In General:

- *Required margins: at least 1.0 cm on the upper and lower margin and at least 1.5 cm on the left and right sides. All tables and listings will be landscape and centered format. All figures will be landscape and centered format, unless portrait orientation suggests that the information presented is easier to interpret.*
- *All output should have the following header at the upper left margin:*
<Sponsor>
Protocol No.: <Protocol No.>
and the following header at the upper right margin:
<Draft/Final Version>, ddmmmyyyy
Page n of N
- *Tables/appendices/listings should be internally paginated (i.e., page numbers should appear sequentially within each table). The name of the SAS program used to generate the output shall be displayed in the lower left corner. SAS Monospace, font size 8 will be used, although the mockup below would indicate differently.*
- *Tables of Contents will be generated separately for Tables and Listings, listing numbers and titles. A file separate from Tables and Listings output must be produced. TOC pages will bear the standard header.*

Tables in general:

- *Each table will present all types of renal function in separate columns and next to each other. If necessary, add a column for total.*
- *If applicable tables will be repeated by treatment (Control, GBCA-Overall, Gadobutrol, Gadodiamide, Gadopentetic acid, Gadoteric acid, Gadoversetamide, and Gadoxetic acid) and by treatment and dose (single/multiple) separately.*

Data Listings in general:

- *All Listings should be - paged by treatment and sorted by renal function, subject and actual date and time.*

Use the appropriate table type as shown below. For more detail description refer to NLS Catalog for Mock ups to support the SAP.

Sponsor Name: Navitas Life
Sciences GmbH
Statistical Analysis Plan (SAP)
Version No.: Final 1

Date: 31JUL2019

Short Title of Study: Long-Term Retention of
Gadolinium in Bone
Sponsor Study No.: ALS-Gd64/001
NLS Study No.: 665

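### SAP 8.5 counts AEs of unknown relationship as GBCA-related without limiting the rule to exposed subjects, so a never-exposed control could be tabulated with a GBCA-related event (minor)

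*SAP*

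**What the plan says.** The rule is in SAP 8.5: "AEs with unknown relationship to GBCA will be counted as related in AE summary tables". It carries no restriction by treatment group. The same section opens with a general statement that points the other way: "There will be no imputation of missing data. All data will be analyzed as they appear in the data base".

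The control group is unexposed by construction. The protocol's eligibility criterion for it reads "Patient has never received GdCA before the scheduled orthopaedic surgical procedure", and SAP 8.9 defines Control as "Includes GBCA naïve subjects".

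Controls are in the safety analysis set, because SAP 8.3 defines that set by surgery and not by exposure: "All subjects who have undergone the planned orthopedic surgical procedure". SAP 9.7 analyses AEs on this set.

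SAP 9 has all tables programmed for the control group as well as for the pooled and individual GBCA groups. The general table instructions in SAP 17 name the treatment pages as "Control, GBCA-Overall, Gadobutrol, Gadodiamide, Gadopentetic acid, Gadoteric acid, Gadoversetamide, and Gadoxetic acid", introduced by the qualifier that tables are repeated where applicable.

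The AE summary in SAP 9.7, presented by treatment, has a line for AEs related to past GBCA exposure. SAP 14 also lists Table 14.7.3, "GBCA Related Adverse Event by System Organ Class and Preferred Term", and Table 14.7.5, its counterpart for serious events.

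At the investigator's end, Protocol 6.2.4.2 lists four possible causes for each AE. The third is "related to GdCA exposure in the past (e.g. NSF signs after enrolment"). The investigator must call each AE unrelated or related; the text offers neither an unknown nor a not-applicable answer.

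**The concern.** Counting an unknown relationship as related is a sensible worst-case convention for a patient who had the product. A control has no exposure to be cautious about, so the same convention yields a statement that is false by definition. No passage in either document sets the relationship to unrelated or not applicable for controls.

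What is at stake is the credibility of the safety tables. Controls serve as the unexposed reference in a study requested by the CHMP, and serious adverse drug reactions are among the AEs of interest in Protocol 6.2.4. A GBCA-related event, particularly a serious one, on the Control page would have to be explained away. The planned control columns are small, so a single case would stand out as a percentage.

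**Working it through.** **Group sizes.** The inputs are the minimum cell targets in Protocol Table 1 (repeated in SAP Table 1) and the control targets in Protocol 8.1.11 and SAP 8.6.

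- Exposed: 2 agents × (5 + 3 + 5 + 3) + 4 agents × (5 + 0 + 5 + 3) = 32 + 52 = 84.
- Controls: 3 × 5 = 15 in the protocol; 5 + 10 = 15 in SAP 8.6.
- Total: 84 + 15 = 99, which reproduces the plan's minimum.

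There is no power calculation to check, because the study is descriptive.

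**Does the rule reach a control?**

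| Step | Source | Result |
|---|---|---|
| Are controls in the AE analysis? | SAP 8.3, 9.7 | Yes; the set is defined by surgery |
| Are AE tables produced for controls? | SAP 9; SAP 17 | Yes under SAP 9; SAP 17 adds a where-applicable qualifier |
| Is the rule limited to exposed subjects? | SAP 8.5 | No |
| Are controls exempted elsewhere? | Protocol 6.2.4; SAP 8.9, 9.7, 10 | No |
| Can a relationship be unknown? | Protocol 6.2.4.2 | Only through an incomplete entry |
| Which text governs in a conflict? | SAP 10 | The SAP |

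The rule speaks of AE summary tables. Table 14.7.1, the AE summary, is plainly covered. Coverage of Tables 14.7.3 and 14.7.5 is the natural reading, since SAP 9.7 describes those tabulations as summaries too, but it is not spelled out.

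**Size if it happens.** The number of controls with at least one such AE is not in the documents, so k is illustrative. The percentage is k divided by the planned column size.

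| k | All controls (15) | Normal renal function (5) | Impaired renal function (10) |
|---|---|---|---|
| 1 | 6.7% | 20.0% | 10.0% |
| 2 | 13.3% | 40.0% | 20.0% |
| 3 | 20.0% | 60.0% | 30.0% |

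The value that makes sense in every cell is not applicable, or zero.

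**Chance that it happens at all.** Assume each of 15 controls independently has probability p of at least one AE whose GBCA relationship is still missing at lock. Then P(at least one affected control) = 1 − (1 − p)^15. The values of p are assumptions.

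| p | P(at least one of 15) |
|---|---|
| 1% | 14% |
| 2% | 26% |
| 5% | 54% |
| 10% | 79% |

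With the rule limited to exposed subjects, the imputed count in controls is 0/15 whatever p is.

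**The case against.** The strongest reply is that the trigger should be rare. Protocol 6.2.4.2 makes the related/unrelated judgement mandatory, and for a never-exposed patient the correct answer is available: unrelated. A missing value would be a breach of that section. It would also have to survive the 100% source data verification in Protocol 9.3, the clarification forms in Protocol 9.1.3 and the cleaning that SAP 12 requires before lock. This stands, and it is why the point is minor. It does not remove the point, because the SAP wrote a rule for unknown relationships and therefore allows that some may remain.

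A second reply is that the qualifier in SAP 17 lets a programmer drop the Control page from GBCA-related tables. That is discretion and not a rule; SAP 9 says all tables, and the line in Table 14.7.1 would remain anyway. It is also fair to say that any such case would be recognisable as a control in the AE listing.

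A reader might infer three stronger things, none of which the documents support:

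- *That sites will leave this field blank for controls.* The eCRF is not among the documents, and its fields and edit checks are unknown.
- *That the rule shrinks an exposed-versus-control difference.* SAP 8 plans no hypothesis tests, and SAP 10 replaces the protocol's comparison against control with side-by-side tabulation. The same rule also raises counts in exposed patients, so the direction of any effect would depend on missingness that is not reported.
- *That the expectedness line in SAP 9.7 is inflated as well.* The rule imputes relationship, not expectedness. That line is merely without meaning for controls, since Protocol 6.2.4.2 judges expectedness for GdCA-related events against the label of the product the patient received.

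**Conclusion.** The point holds in conditional form. As written, SAP 8.5 would convert a missing GBCA relationship in a control into a GBCA-related AE, which is impossible for a patient who meets the control definition. Table 14.7.1 is certainly affected; Tables 14.7.3 and 14.7.5 are affected on the natural reading.

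The size rests on two assumptions: that at least one such entry survives cleaning, and that the control columns are at their planned sizes. One affected control then gives 6.7% overall, or 20% in the normal-renal-function column. The sizes of 15, 5 and 10 are targets, and achieved numbers would shift these figures.

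Severity is minor. The consequence is confined to descriptive safety tables and leaves the Gd concentration results in bone and skin untouched.

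**What to change.** 1. Reword the rule in SAP 8.5 along these lines: *In GBCA-exposed subjects, an AE whose relationship to GBCA is unknown is counted as related. In GBCA-naïve controls, relationship to GBCA is reported as not applicable.* Mark this as an exception to the no-imputation statement that opens the section, so that the two no longer conflict.
2. In Table 14.7.1, show the GBCA-related and expectedness lines as not applicable for Control. Omit Control from Tables 14.7.3 and 14.7.5.
3. Before database lock, query any control AE actually recorded as GBCA-related, as a possible error in exposure history. Keep the value as recorded in the AE listing so that step 1 does not hide it. A confirmed exposure would contradict the control eligibility criterion and belongs in the protocol deviation review of SAP 8.4.

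The cost is a sentence or two in the SAP, one programming condition and a short data check. Exposed patients keep the full worst-case rule, so no caution is lost where it has a purpose.
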